6. SUBJECTS

6.1 Anticipated number of research subjects

Since there is no pilot data to base an *a priori* sample size calculation on, it is difficult to make a calculated prediction on the exact number of patients required for a sufficiently powered trial. The outcome of this present study will inform the power calculation for a larger definitive interventional trial. However, below a summary is given for the power potentially achievable for our suggested feasibility sample size. Since some patients may require surgical intervention or may withdraw, a hypothetical 30% dropout rate is calculated into the sample size (actual attrition rate is a study objective). A 1:1 allocation to the control and intervention group respectively will be applied.

The primary outcome, average percentage decrease in ulcer size is used for sample size calculation. Power calculations for sample size, 80% power and 5% significance, based on a Chi-squared test. A priori power calculations using GPower 3.1 software, result in the following sample size summarized in Table 4.

It must be stressed that this current PREVUE study will first and foremost establish if StepIt exercise is acceptable to staff and patients alike, and therefore it is not certain at this stage whether sufficient participants will be enrolled, if participants will be compliant and if they will be compliant for the 12 weeks treatment period.

Table 4, Sample size calculation

	Percentage patients achieving at least 50% reduction in ulcer size	Percentage patients not achieving 50% reduction in ulcer size		
Arm A (hypothetical)	60%	40%		
Arm B (hypothetical)	30%	70%		
	Power beta of 80%, Alpha p-value of 0.05, Effect size 0.6 Sample size required without any drop-out: 22 samples. Sample size with 30% attrition rate included: 28			
	Total of 28 patients: - 12 Patients to receive treatm - 12 Patient to receive treatment	nent as usual ent as usual plus Steplt exercise		

The CONSORT guidelines require a statement on the number of patients assessed for eligibility (Schulz, Altman & Moher 2010). The number of patients screened but who did not meet the inclusion criteria or who declined to participate will be recorded, as will any patients who are lot to follow-up (Appendix 3).

The calculation does take into account a 30% patient attrition rate (withdrawal and loss to follow-up), since this involves a study with at least two visits. Patients will be recruited from the adult (age 18+) population routinely seen by the evaluating clinical staff members.

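### Table 4's 80% power does not follow from its own rates: 60% versus 30% in two equal arms is effect size w = 0.30, not 0.6, so 22 patients give about 29% power

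*Protocol*

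**What the plan says.** Section 6.1 explains that there are no pilot data, and offers an illustration of the power the proposed feasibility sample might achieve. The basis is given as "Power calculations for sample size, 80% power and 5% significance, based on a Chi-squared test", run in GPower 3.1. On allocation it says "A 1:1 allocation to the control and intervention group respectively will be applied".

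Table 4 sets out hypothetical rates of at least a 50% reduction in ulcer size: 60% in Arm A and 30% in Arm B. Below them it states "Power beta of 80%, Alpha p-value of 0.05, Effect size 0.6 Sample size required without any drop-out: 22 samples". It then gives "Sample size with 30% attrition rate included: 28" and "Total of 28 patients", so 22 and 28 both count patients over the two arms together.

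Section 5.5.2 names ulcer size as the outcome behind this power calculation. Section 8.2 makes signs of clinical effectiveness one of the considerations in deciding whether a larger trial is indicated, and allows that a large enough effect could settle the effectiveness question within this study.

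**The concern.** Cohen's w for a 2x2 table depends only on the cell proportions, so the two rates and the 1:1 allocation fix it. A 30-point difference centred on 45% cannot give a two-arm w as large as 0.6. A w of that size corresponds, for example, to 80% versus 20%.

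If the effect size is wrong, so is the only power figure in the protocol. The 22, and the 28 derived from it, then rest on a calculation for a different problem. Two uses are exposed:

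- **Interpreting this trial.** Someone who believes power is 80% may read the absence of an efficacy signal as evidence against the device, and section 8.2 lets that signal bear on whether a full trial follows.
- **Planning the next trial.** Section 6.1 says the results will feed its power calculation. If the same method were reused for a two-arm binary comparison at these rates, that trial would be about fourfold too small.

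**Working it through.** **Inputs (all from Protocol 6.1 and Table 4):** rates 0.60 and 0.30; 1:1 allocation; chi-squared test; alpha 0.05; power 0.80; effect size 0.6; 22 in total before dropout; 28 in total after it. Degrees of freedom are not stated; a two-arm binary comparison has df = 1. The test is non-directional, so it is equivalent to a two-sided test.

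**Step 1: reproduce the stated 22.** Power is the upper tail of a noncentral chi-squared distribution with df = 1 and noncentrality N × w², beyond the 5% critical value of 3.84.
- w = 0.6, N = 22: noncentrality 22 × 0.36 = 7.92; power 80.4%.
- 22 is the smallest N reaching 80%. The table's figure is therefore exactly what w = 0.6 produces.

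**Step 2: derive w from the stated rates.** For equal arms, w = (p1 − p2) / (2 × √(p̄(1 − p̄))), with p̄ = (0.60 + 0.30)/2 = 0.45.
- w = 0.30 / (2 × √(0.45 × 0.55)) = 0.3015, about half the stated value.

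**Step 3: where 0.6 may come from.** The protocol does not say. Two other quantities lie close to it:
- Cohen's h for two proportions: 2·asin(√0.6) − 2·asin(√0.3) = 0.613.
- A one-sample goodness-of-fit w, treating 60/40 as known and 30/70 as observed: √(0.09/0.6 + 0.09/0.4) = 0.612.

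Neither is a valid w for comparing two randomised arms. This origin is inference, and the error does not depend on it.

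**Step 4: power at the correct w.** At N = 22 the noncentrality is 22 × 0.0909 = 2.0.

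| Total evaluable | Why this number | Power for 60% v 30% |
|---|---|---|
| 19.6 | 28 less 30% | 27% |
| 22 | Table 4 before dropout | 29% |
| 24 | two arms of 12, as listed in Table 4 | 31% |
| 28 | Table 4 total, no dropout | 36% |
| 44 | if 22 were per arm | 52% |
| 48 | total in the lay summary | 55% |

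Exact enumeration agrees. The uncorrected Pearson test has power 25%, 30%, 36% and 33% at 10, 11, 12 and 14 per arm; it is not monotone because the data are discrete. Fisher's exact test at 11 per arm has 16.5%.

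**Step 5: sample size for 80% power.**
- Noncentral chi-squared, w = 0.3015: 87 in total.
- Pooled normal formula: (1.96 × √(2 × 0.45 × 0.55) + 0.8416 × √(0.60 × 0.40 + 0.30 × 0.70))² / 0.30² = 41.97, so 42 per arm, 84 in total.
- With continuity correction: 49 per arm (98). One-sided: 33 per arm (66), or 40 per arm (80) with correction.

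No variant comes near 22. Allowing for 30% dropout, 84/0.7 = 120 and 87/0.7 = 124.3, so about 120 to 125 would have to be recruited.

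**The case against.** The best defence is that this is a feasibility trial. Its primary objective is not efficacy, the rates are labelled hypothetical, the text admits there are no pilot data, and section 5.5.2 calls the efficacy results preliminary. A trial of 28 needs no 80% power for efficacy, and correcting the table changes no patient, visit or endpoint. That limits the consequences and is why no larger sample is asked for. It does not make the number right: the protocol prints an a priori 80% power, derives 22 and then 28 from it, and lets effectiveness signals inform the decision on a larger trial.

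A second objection is that the chi-squared responder test is not the planned efficacy analysis. Section 8.3 compares ulcer size by Mann-Whitney test on differences between time points. This stands as a limit on scope. The powers above belong to the comparison in Table 4; the power of the planned test cannot be worked out from the document.

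Third, the warning about a misread null result is a prediction about readers. The remark in section 8.2 about settling effectiveness is conditional on a large effect, so it concerns a positive result. The risk for a null result comes instead from the use of effectiveness signals in deciding on the larger trial.

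**Conclusion.** The concern holds. Table 4 states 80% power for a design that, at its own rates, has about 29% with 22 evaluable patients and between roughly 25% and 36% over the plausible evaluable numbers (about 20 to 28). The stated effect would be missed about 70% of the time at 22. The required number is understated about fourfold: 22 against 84 to 87.

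This rests on a two-arm comparison with df = 1, a 5% non-directional chi-squared test and 22 being a total, which Table 4's own total of 28 supports. The exact percentage varies by a few points with the method, and is lower still with Fisher's test; the conclusion does not change. The feasibility aim itself is not invalidated.

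**What to change.** In section 6.1 and Table 4:

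1. Delete the 80% power statement, the effect size of 0.6 and the 22.
2. Say that the sample is chosen for feasibility. If power is mentioned, state that a two-arm chi-squared comparison of 60% v 30% has roughly 25% to 36% power at the planned size, or that 22 evaluable patients give 80% power only for a contrast of about 80% v 20% (w = 0.60 / (2 × √(0.5 × 0.5)) = 0.6). Make clear that this describes the responder comparison, not the Mann-Whitney analysis in section 8.3.
3. Justify the number by the precision of the feasibility rates. As an illustration, 8 of 28 patients lost would give a Wilson 95% confidence interval for attrition of 15% to 47%.

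The cost is protocol wording only. The stated power becomes less favourable; no patients, visits or procedures are added.

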6.1.1 Randomisation

Following written consent patients will be allocated at random to the control or intervention group, using a non-restricted randomised sequence generated for the whole sample using a free ware randomisation programme, see https://www.randomizer.org/. The randomisation will be stratified for VLU size, with one group being those with a PUSH score of 8 or lower and the other with a PUSH score of 9 or higher. Sequential envelopes with each next randomisation allocation will be used to achieve concealment. It is recognised that random selection does not guarantee representativeness but variables which may affect the outcome variable are more likely to be balanced out and reliability enhanced (Thomas 1990).

As the study involves a self-administered intervention of necessity it is not possible to achieve blinding for the participants. Due to the pilot nature of this study, the researcher will not be blinded either to the subjects intervention, although this can be considered as part of a larger trial since it would further reduce any risk of bias. However, the primary outcome measure, size of the VLU is a quantitative outcome measure which is less prone to bias than for example a patient reported outcome measure or a clinician reported outcome measure.

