PREVUE v4, dd 12Dec2018

PREVUE; PlantaR flexion Exercise for Venous Ulcer Evaluation, a multi-centre, controlled, prospective, randomized feasibility trial

Version 4, dd 12 December 2018

Chief Investigator's Statement of Ownership and Content.

I, [name], confirm that this protocol is my work and is owned by me. The protocol conforms with standards outlined in the Declaration of Helsinki 1964.

Name (PRINT):___[name]_____

Signature:

Date: ____12 Decl 2018_____

RESEARCH PROTOCOL SUMMARY

TITLE:	PREVUE; PlantaR flexion Exercise for Venous leg UlcEr, a multi- centre, controlled, prospective, randomized feasibility trial
Short title:	PREVUE
IRAS number	222694
Device description	StepIt plantar flexion rocker pedal device. CE-marked and licensed medical device. To be used in this study for indicated purpose, namely plantar flexion exercise.
Study design	Single centre, controlled, prospective randomized feasibility trial
Primary objective	To assess the feasibility of conducting a full RCT in the future - Participants' compliance to StepIt exercise regime
	 Recruitment and attrition rates, willingness of patients to be randomised, response rates to questionnaires, and degrees of missing data Testing of eligibility criteria and ability/willingness of clinical staff to partake in recruitment of participants Adequacy of duration of follow-up (e.g. in relation to VLU healing)
Secondary objectives	To determine the acceptability and efficacy of the step-it pedal as an adjuvant therapy for VLU at 6 and 12 weeks post-baseline - Healing rate (ulcer size, PUSH score) - Ankle motion range - Patient mobility score - VLU-related quality of life score - VLU-related pain - Patient feedback on use of the device
Patient population	A total of 28 participants, over the age of eighteen, with venous leg ulcers and treated either in hospital or at home by the community nursing team. Participants must have the capacity to provide informed written consent and complete patient reported outcome measures. Participants are recruited from the local community nursing caseload and identified in hospital clinics. - 12 Patient will receive treatment as usual (TaU) - 12 Patients will receive TaU plus StepIt exercise programme intervention

	Randomisation will be stratified for ulcer size, with cut-off PUSH
	score of up to 8, and 9 and above.
Sponsor	Cumbria Partnership NHS Foundation Trust
Manufactures O foundan	Charalle Coreboure A.D.
Manufacturer & funder	StepIt System AB,

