1. LAY SUMMARY

Venous leg ulcers (VLUs) are the most common type of leg ulcers, affecting 1-3% of the population over 60 years and this incidence is expected to increase with an aging population. There is some evidence to suggest that specific exercise of the calf muscle through for example plantar flexion movement with resistance — moving the front of the foot up and down, similar to what a drummer does when using the foot pedal of a drum - may improve the calf muscle pump function. The positive effects have been shown at the haemodynamic level; they have shown that at least in the short-term there is better blood flow and endurance if the calf muscle is exercised in this manner.

It is acknowledged that venous return from the lower limbs depends on an efficient calf muscle pump and adequate range of ankle motion. Whilst failure of these systems may contribute to venous leg ulceration, evidence suggests that exercise programmes designed to increase the strength of the calf muscle pump through resistance training is feasible and effective in improving calf muscle pump function and ankle range of motion. As yet there remains considerable uncertainty as to the effects of an exercise programme on ulcer healing. There is very limited research data available on the medium- to long-term effects of calf muscle exercising by VLU patients on the healing rate of the ulcer.

This study is a prospective, controlled, randomised, feasibility trial to determine if the use of a CE-approved plantar flexion pedal, developed by StepIt Ltd, will be of benefit to people with VLU in terms of healing rate of VLUs. This pilot aims to assess the feasibility of conducting a full randomised clinical trial in the future. Of the total of 48 patients to be recruited, 24 patients will be randomised to treatment as usual, standard compression therapy only, and the other 24 will be allocated to treatment as usual plus a StepIt exercise programme for 12 weeks. The main outcome measure will be the degree of healing of the VLU. Other outcomes measures will include acceptability of the device training, trial completion rates, and ankle range of motion. Patients with VLUs are less mobile than their aged matched population for a variety of reasons. Initiating foot and ankle exercises may be a first step in increasing physical activity for this population and improving calf muscle pump function.

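### Allocation is described both as one unrestricted whole-sample sequence and as stratified by PUSH score; as written, the stratification has no effect

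*Protocol*

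**What the plan says.** Protocol section 6.1.1 gives the method in consecutive sentences. Patients are allocated "using a non-restricted randomised sequence generated for the whole sample using a free ware randomisation programme". Then: "The randomisation will be stratified for VLU size, with one group being those with a PUSH score of 8 or lower", with the other group at 9 or higher. The protocol summary repeats the second statement: "Randomisation will be stratified for ulcer size, with cut-off PUSH" of up to 8 against 9 and above.

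Concealment is described once: "Sequential envelopes with each next randomisation allocation will be used to achieve concealment". The protocol does not mention blocks, minimisation, a list per stratum or an envelope set per stratum.

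On the ratio, section 6.1 says "A 1:1 allocation to the control and intervention group respectively will be applied". The summary has "A total of 28 participants, over the age of eighteen, with venous leg ulcers", and both the summary and Table 4 list two arms of 12. The lay summary has "Of the total of 48 patients to be recruited, 24 patients will be randomised to treatment as usual".

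Section 8.3 compares changes in ulcer size, PUSH score and pain between arms by Mann-Whitney tests without reference to the stratum. It adds a Cox model, with baseline ulcer size among the covariates, only if there are enough data.

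**The concern.** The two sentences describe different procedures. Someone preparing the envelopes cannot follow both, and someone opening them cannot tell whether a patient with a PUSH score of 9 draws from a common queue or a separate one.

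A second reading, one unrestricted list per stratum, removes the verbal conflict but not the problem. Stratification balances a factor only if allocation within each stratum is restricted, for example by blocks.

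Baseline ulcer severity is the only factor the design sets out to control, and ulcer size and PUSH score are also outcomes. Section 8.2 lets signs of clinical effectiveness inform whether a larger trial is run, and allows that a large effect might settle the question. A chance difference in severity would weaken that reading. Section 5.5.1 also counts the ability of sites to randomise among the primary feasibility outcomes, so the procedure itself is under test.

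**Working it through.** **Inputs.** Unrestricted sequence, two PUSH strata and 1:1 ratio: sections 6.1.1 and 6.1. Total N: 28 (summary and Table 4), 24 (the sum of the two arms of 12) or 48 (lay summary). Share of patients with PUSH 9 or higher: not given; taken as 30% to 50%.

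**The plan's own figure.** The protocol gives no figure for balance. Its total can be traced: a chi-squared test with 1 degree of freedom, effect size 0.6 and alpha 0.05 has power 0.785 at 21 patients and 0.8035 at 22, so 22 is reproduced. 22 × 1.3 = 28.6, against the stated 28. Whether 0.6 is the right effect size is a separate matter. 28 is used as the main case.

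**Step 1: does an unrestricted list per stratum help?** In an unrestricted sequence each allocation is an independent fair toss. Splitting independent tosses into two lists leaves them independent fair tosses, so the distribution of imbalance is the same. In a stratum of n patients the arm difference has SD √n; for n = 14 that is 3.74. Simulation at N = 28 (200,000 trials, half the patients in each stratum on average) agrees:

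| Scheme | SD of arm difference within a stratum | P(difference within that stratum ≥ 4) |
|---|---|---|
| One unrestricted list | 3.75 | 0.351 |
| Unrestricted list per stratum | 3.74 | 0.350 |
| Blocks of 4 per stratum | 0.91 | 0 |

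**Step 2: arm sizes.** With X ~ Binomial(N, 0.5), P(equal arms) = C(N, N/2) / 2^N.

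| N | Equal arms | Arms differ by ≥ 6 | Arms differ by ≥ 8 |
|---|---|---|---|
| 24 | 0.161 | 0.307 | 0.152 |
| 28 | 0.149 | 0.345 (17:11 or worse) | 0.185 (18:10 or worse) |
| 48 | 0.115 | 0.471 | 0.312 |

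**Step 3: balance on PUSH score.** Let s patients have PUSH 9 or higher, with a ~ Binomial(s, 0.5) and b ~ Binomial(N − s, 0.5) the numbers from each stratum in the first arm. The arms' shares differ by |a/(a+b) − (s−a)/(N−a−b)|. Summing the exact probabilities of a difference of at least 0.20:

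- N = 28, s = 14 (50%): 0.346; if s itself varies around 50%, 0.318.
- N = 28, s = 8 (about 30%): 0.265; if s varies around 30%, 0.261.
- N = 48, s = 24: 0.194; s = 14: 0.142.

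With s = 14 at N = 28, both strata split exactly evenly with probability (3432/16384)² = 0.044.

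**Step 4: what restriction would achieve.** With blocks of 4 per stratum (an assumed size), arms cannot differ by more than 2 within a stratum or 4 overall. At N = 28, P(overall difference ≥ 6) falls from 0.345 to 0, and no simulated trial had a 20-point difference in PUSH share.

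**Step 5: what an unequal split costs.** Precision relative to 14:14 is 4·n₁·n₂/N². At 17:11 it is 4 × 17 × 11 / 784 = 0.954; at 18:10 it is 4 × 18 × 10 / 784 = 0.918.

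**Step 6: what blocking costs.** Suppose a recruiter knows earlier allocations in a 14-patient stratum and always guesses the arm that is behind. In simulation the guess is right about 72% of the time with blocks of 2 and 4 mixed equally and about 68% to 69% with blocks of 4 and 6, against 50% under simple randomisation.

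**The case against.** The strongest reply is that simple randomisation is valid. It leaves the comparison unbiased and the rank tests sound, and no primary feasibility outcome depends on balance. This stands, and it limits the point to precision and credibility on secondary outcomes.

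A reader might infer that the protocol fixes exactly equal arms and that an unrestricted sequence therefore breaks it. The text does not support that. Section 6.1 states a ratio, which simple randomisation meets in expectation, and the two arms of 12 do not add up to the stated 28, so they are weak evidence of a binding split. Unequal arms also cost little: a 17:11 split keeps about 95% of the precision.

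It can also be said that section 8.3 analyses changes rather than final values and plans a Cox model with baseline ulcer size. That is partly an answer. A change score is not an adjustment for the stratum, and the Cox model is conditional on sufficient data.

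Two replies bear on the remedy. Section 5.4 has the visiting researcher randomise the patient, and section 6.1.1 leaves the researcher unblinded, so the predictability in Step 6 is a real concern; simple randomisation, stated plainly, is a defensible choice. And the protocol version is dated 12 December 2018 while Table 2 ends recruitment in Dec-18, so few or no allocations may remain. Both stand and shape the fix.

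None of this reconciles the two sentences or makes the stratification work. Nor is it detail left for an analysis plan: the protocol fixes the method itself, and a list has to exist before the first patient is allocated.

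**Conclusion.** The point holds as an internal contradiction that defeats its own purpose, and it should be fixed. One unrestricted whole-sample sequence is not stratified, and unrestricted lists per stratum balance PUSH score no better than none.

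At N = 28 equal arms occur in about 15% of trials, and a difference of at least 20 points in the share with PUSH 9 or higher in roughly 26% to 35%. The first figure needs only the unrestricted sequence; the second also rests on the assumed 30% to 50% in that stratum. At N = 48 equal arms are rarer (11.5%), but a 20-point difference in share is less likely (about 14% to 19%).

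A reader might go further and conclude that the treatment comparison is biased or the trial invalid. The documents do not support that: the imbalance is due to chance, and it bears on secondary outcomes described as preliminary.

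**What to change.** Reconcile section 6.1.1 and the summary.

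- **Allocations still to be made.** Either keep the stratification and make it work, or drop it. To keep it: a separate concealed list for each PUSH stratum, in permuted blocks of varying, undisclosed size, avoiding blocks of 2; a separate set of sequentially numbered, opaque, sealed envelopes per stratum; all prepared by someone who does not enrol patients. To drop it: delete the stratification statements and say that simple randomisation is used.
- **Allocations already made.** State how the list was actually generated and whether the envelopes were kept separate by stratum.
- **Analysis, in every case.** Account for the PUSH stratum in the between-group comparisons in section 8.3, for example with a stratified (van Elteren) rank test. This is valid whichever way the list was produced.

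The wording and the analysis change cost almost nothing, and a new list needs only a free tool. The real cost is predictability: blocking lets an unblinded recruiter who knows earlier allocations guess right roughly 70% of the time instead of 50%. Larger blocks reduce this only slightly, at the price of looser balance (blocks of 4 and 6 cap the arm difference at 3 per stratum, against 2 with blocks of 4). The choice between blocking and simple randomisation should be made with that in view and the reason recorded.
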